2.2 Significance

2.2a. Overall significance of the current proposal: Given the sheer numbers of patients afflicted with septic shock each year, and the current mortality rates despite advances in early aggressive treatment and sophisticated critical care, new targets are needed in the armamentarium against this disease. With the ageing of the U.S. population, it is anticipated that the incidence of sepsis and septic shock will only increase¹, adding to the urgency to identify an intervention to improve outcomes and reduce disease burden amongst survivors.

2.2b. Innovation: The current proposal is innovative in that it leverages an existing therapeutic agent for a new indication, building on existing data supporting the concept of beta-adrenergic antagonism in septic shock. If the promising findings reported in the recent single center study from Italy⁶ could be confirmed in a pilot study in a septic shock cohort in a typical U.S. tertiary care medical center, the science of the resuscitation of septic shock could be considerably advanced. Esmolol, which is already used in practice in other clinical scenarios in critical care, could easily be incorporated into the treatment of patients with septic shock, if the balance of evidence ultimately indicates benefit in this population. In addition to evaluating the effects of esmolol on hemodynamics, our proposal is innovative in that we will also directly measure continuous VO_2 in the subset of patients who are mechanically-ventilated in order to better understand how beta blockade therapy will affect overall oxygen consumption in a septic shock population, which to our knowledge has not been previously examined in this way.

B3. DESCRIPTION OF RESEARCH PROTOCOL

[figure not shown]
A. Study Design – Overview, Methods, Procedures

Study Design: A Multi-center, open-label, randomized, phase II trial comparing esmolol to standard care (no esmolol) in septic shock patients with tachycardia.

Screening: All patients admitted to the ICU will be identified through electronic patient records and screened for possible enrollment by trained research assistants. Our research group employs multiple full-time research assistants responsible for screening and enrollment. With this staffing structure, we are able to enroll patients 24 hours per day/7 days per week.

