Consent: If a patient meets all of the inclusion criteria and none of the exclusion criteria, a member of the research team will approach the patient for written informed consent. If the patient is unable to consent, a legally authorized surrogate may be approached per standard IRB procedures. Investigators will explain the study's background and significance, potential risks and benefits, and study protocol. In the event that a physician Investigator or a surrogate is not physically present in the hospital to perform the consent process, a non-physician study staff (research assistant or research coordinator) will coordinate a conference (i.e. FaceTime or Skype video conferencing or telephone) for the physician investigator / surrogate to join in the consent discussion. If consent is obtained, a signed copy will be given to the patient and another copy placed in the medical record. The original signed informed consent will be kept in our locked research office (see specifics in **Section B6 - Recruitment and Consent Procedures**).

Randomization: The randomization will be done in a 1:1 ratio between treatment and control groups in varying blocks of two to six using SAS software. This main list of group assignment will be maintained in the hospital research pharmacy.

Study Arms: After randomization as described above, patients will be assigned to one of the following two arms: esmolol for 24 hours or standard care (no esmolol).

1) Esmolol for 24 hours: Patients in this arm of the study will have Esmolol for 24 hours.

2) "Usual Care": Patients will receive 100 mL of normal saline over 5-10 minutes at the beginning of the study in addition to usual care. When patients are enrolled in a clinical trial there is a time period from consent to study drug administration that depends on the investigative team, the research pharmacy, and the available nursing staff. In order to guarantee that this time interval is similar between the two groups the control arm will receive a small bolus of saline at the beginning of the trial. This will ensure that "time zero" is similar between the two groups.

Blinding: The study will not be blinded as an esmolol infusion must be actively titrated to effect by clinicians and it will noticeably decrease heart rate.

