review and report all adverse events to the Committee on Clinical Investigation (CCI) according to the adverse event reporting policy of the CCI.

All biological material will be stored in a locked refrigerator/freezer within a locked facility, which is under hospital security surveillance at all times. All electronic records will be maintained on BIDMC IS compliant computers.

B7. STUDY LOCATION

Privacy

In order to maintain privacy, the investigators will discuss the study and consent the subjects in a private area in-hospital. Standard clinical protocols regarding patient confidentiality will be followed during the course of the study. The collection of sensitive information about subjects is limited to the amount necessary to achieve the aims of the research.

Physical Setting

The study will take place in the Emergency Department and ICUs at Beth Israel Deaconess Medical Center and Lahey Hospital & Medical Center in Burlington Massachusetts.

B8. DATA SECURITY

All hard copies of study data will be kept in a locked filing cabinet to which only the PI and co-investigators will have access.

All electronic data will be stored on the BIDMC secure server behind a firewall in a password-protected database. We will also utilize the database application, REDCap. REDCap is a professional database endorsed by the National Institutes of Health (through the clinical and translational science award) that provides a secure, user-friendly database with capacity for easy statistical analysis. The program can support multiple research studies, is presently being used at dozens of major academic research centers to support numerous NIH and AHA funded projects and is available for free at our center.

B9 Multi-Site Studies

Is the BIDMC the coordinating site? Yes No

Is the BIDMC PI the lead investigator of the multi-site study? Yes No

Coordinating Center (BIDMC) Responsibilities: The trial will be directed by the Principal Investigator, who will have responsibility for receiving and analyzing data for the trial, and will oversee all functions. We will provide the other institutions with documents to use and communicate procedures.

As the coordinating center for this multicenter trial, [name] assumes full responsibility for ensuring all aspects of the study are conducted appropriately. This will be achieved via the following mechanisms, under the direction of [name]:

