12. As part of our on-site visit, we will include a Lahey Hospital & Medical Center Research Pharmacy review to assess the following: documentation of secure drug storage; drug accountability from receipt of drug through all dispensing and ultimately destruction on drug accountability logs; documentation of performance of regular inventory verification; confirmation that orders for research medication are written only by authorized prescribers on the 1572 form or delegation of authority log; confirmation that study drug must have continuous temperature monitoring and recorded at least daily on temperature logs (minimum, maximum, current); verification of drug destruction per Lahey Hospital & Medical Center internal policy. The BIDMC Research Pharmacy will be available to answer questions as they may arise from the Lahey Hospital & Medical Center Research Pharmacy.
13. A formal site monitoring report will be provided to Lahey Hospital & Medical Center and the CCI after each site visit. This report will include data on the number of charts reviewed, discuss any identified deficiencies and any corrective actions taken. The Lahey Hospital & Medical Center site PI will then provide this report to their local IRB in accordance with local IRB reporting requirements.

Database Management: The coordinating center (BIDMC) will be responsible for developing the online database (see section 4.4), including a shared database with common data definitions. All forms and data dictionary will be available online for all individuals who perform data entry.

All sites will enter de-identified data into the electronic database. Data entry will be done via REDCap. Discrepancies or missing data points will be identified through a data review process by the coordinating center resulting in queries sent to the participating sites for resolution. Changes will be made in REDCap by each participating site.

The coordinating center will oversee and instruct sites on specimen collection and separation. Sites will be provided with detailed instructions for laboratory processing. All sample types will be processed initially on site, separated by centrifugation if necessary, dispensed into aliquots if required, and kept frozen (preferable at -80°) until shipment to the Center for Resuscitation Lab .

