AMENDMENT DESCRIPTION- REQUIRED FOR ALL SUBMISSIONS

A detailed description of the amendment, in your own words, **MUST** be provided below. The PI may provide a summary of a lengthy sponsor amendment in an attached cover letter or memo, however this should not simply be a copy of the sponsors amendment and/or letter. Either list the current item followed by the new item, or attach a redlined version of the changed document. If the consent form is revised, attach one copy of the consent form in which the changes (including additions and deletions) are clearly highlighted, and one clean copy of the consent form.

Change in participating study sites: One study site (Henry Ford Hospital) is being removed and one additional study site (Lahey Hospital & Medical Center) is been added.

PI Memo/Cover Letter Describing Changes is attached Sponsor Letter Describing Changes is Attached

Impact on Budget/Funding

Does this amendment affect the current budget for the study?  No  Yes, if yes, explain and contact: - Clinical Trials Office for Industry Funded Studies - Office of Sponsored Programs for Other Funding Sources	Does this amendment affect the current funding for the study?  No  Yes, if yes, explain and contact: - Clinical Trials Office for Industry Funded Studies - Office of Sponsored Programs for Other Funding Sources
---	--

AMENDMENT RATIONALE- REQUIRED FOR ALL SUBMISSIONS

The reason or justification for the changes **must** be discussed as well as how the change might affect the risk/benefit ratio. Please also address how or if a change in the risk/benefit ratio impacts the informed consent form, and if the change necessitates a change in the consent form. The rationale may be provided **here** or in an attached cover letter or memo.

Change in participating study sites: Henry Ford Hospital in Detroit Michigan will no longer participate as a study site for our study. Lahey Hospital & Medical Center being added to increase the enrollment speed. We will not be increasing the global number of enrollment.

These changes do not affect the risk/benefit ratio. This study **DOES NOT** necessitate a change in the written, informed consent form.

PI Memo /Cover letter Describing Rationale is Attached Sponsor Letter Describing Rationale is Attached

Signature of Principal Investigator

Date

[name]
Print Name

AMENDMENT FORM

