The association between continuous infusion of esmolol and need for vasopressor support was assessed by comparing the median 6 hour norepinephrine equivalent dose (NED) between groups using a Wilcoxon rank-sum test. No patients expired prior to 6 hours after enrollment. To analyze the difference in vasopressor dose between groups at 12 hours and over time, we compared NED (recorded hourly for 12 hours) over time between groups using linear mixed effect models accounting for repeated measures and adjusting for pre-intervention NED. The appropriate variance-covariance structure was selected based on Akaike information criterion. Using this model, we tested whether NED was different at 12 hours and for differences in the overall trend over time. A similar analysis was used to assess the difference in heart rate between groups over the first 12 hours and lactate between groups over the first 24 hours; however, in the heart rate analysis, we tested for mean differences at 6 hours, 12 hours and for differences in the overall trend over time, and in the lactate analysis, we used a log-transformed lactate value to test for mean differences at 12 and 24 hours and for differences in the overall trend over time. We compared the median number of shock free days, defined as cessation of all vasopressors during the first 7 days, between the two groups.

To characterize the effects of esmolol infusion on VO_2 , we limited the analysis to patients who were mechanically ventilated during the study period. The VO_2 values were cleaned based on a custom algorithm that eliminated points that met any of the following four criteria: 1) VO_2 value corresponding to a Fraction of Inspired Oxygen (FiO_2) value above 61%. 2) VO_2 value within 10 minutes of a 10-unit change in FiO_2 . 3) VO_2 value above 800 mL/kg/min or below 80 mL/kg/min that is not sustained for at least 30 consecutive minutes. 4) VO_2 value that is 15% higher or lower than the average of the VO_2 values 5 minutes before and after the point in question.

To analyze the difference in oxygen consumption between groups at 12 hours, 24 hours and over time for patients who were on mechanical ventilation at enrollment, we compared VO_2 measurements (standardized by bodyweight in kilograms) over time (recorded every minute

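### Site enters neither the described randomisation nor any SAP analysis, and allocation at the second hospital is not described; the cost is precision and chance imbalance, not bias

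*Protocol*

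**What the plan says.** Protocol B3, Study Design, describes the trial as follows: "A Multi-center, open-label, randomized, phase II trial comparing esmolol to standard care (no esmolol) in septic shock patients with tachycardia". The Randomization paragraph of B3 gives the whole method: "The randomization will be done in a 1:1 ratio between treatment and control groups in varying blocks of two to six using SAS software". It adds: "This main list of group assignment will be maintained in the hospital research pharmacy". No stratification factor is named there or elsewhere in the supplied text.

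Section B7, Physical Setting, places the study at "Beth Israel Deaconess Medical Center and Lahey Hospital & Medical Center in Burlington Massachusetts". The amendment form that added the second hospital gives the reason: "Lahey Hospital & Medical Center being added to increase the enrollment speed. We will not be increasing the global number of enrollment". Section B9 plans a "Lahey Hospital & Medical Center Research Pharmacy review" that covers storage, dispensing and accountability, so that hospital dispenses study drug itself. Neither B3 nor B9 says whether its patients are allocated from the main list, from a copy, or from a list of their own.

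Protocol B3, Standard septic shock treatment, leaves management in both arms to the treating team. The primary endpoint is the norepinephrine dose at 6 hours. The SAP analyses it by "comparing the median 6 hour norepinephrine equivalent dose (NED) between groups using a Wilcoxon rank-sum test". The SAP's mixed models for dose, heart rate, lactate, biomarkers and SOFA adjust for the pre-intervention value, and the oxygen consumption model does not. Site appears in none of them.

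**The concern.** The primary endpoint is a dose that clinicians set, at their discretion, in an open-label trial. If the two hospitals wean norepinephrine differently, site predicts the outcome. Blocks on a list shared by two hospitals balance the overall total but not either hospital, because consecutive places in a block can go to different sites. The smaller, later site could then have noticeably more patients in one arm by chance. With no site term in the analysis, that imbalance passes into the treatment estimate and the between-hospital spread stays in the error term. The planned 104 patients give almost exactly 80% power, so there is no reserve to absorb the loss.

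A basic operational step of a two-site trial, how the second site obtains its allocations, is also left unstated.

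**Working it through.** **1. The plan's own figure.** SAP inputs: control mean 0.15, esmolol mean 0.10, SD 0.09 mcg/kg/min, power 80%, type I error 0.05 (taken as two-sided).

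- Normal approximation: n per arm = 2 × (1.960 + 0.842)² × (0.09/0.05)² = 2 × 7.85 × 3.24 = 50.9, so 51 per arm, 102 in total.
- Exact two-sample t-test: 51.84, so 52 per arm, 104 in total, with power 80.1%. The stated 104 is reproduced.
- Standard error of the planned contrast: 0.09 × √(2/52) = 0.0177.

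**2. How uneven the second site could be.** Its share is not in the documents. Assumptions: one shared list, blocks of 2, 4 and 6 chosen at random, and second-site patients falling only in the second half of enrolment because the site was added late. Simulated 95% range of the site's esmolol count:

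- 20 patients: 7 to 13 (6 to 14 if they were spread over the whole trial)
- 30 patients: 11 to 19

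**3. Effect on the arm contrast.** Shift = (esmolol count − control count at the site) / 52 × between-site difference. The between-site difference is not in the documents; 0.05 and 0.09 are assumed.

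| Site split | Difference 0.05 | Difference 0.09 |
|---|---|---|
| 13 v 7 | 6/52 × 0.05 = 0.0058 (12% of 0.05) | 6/52 × 0.09 = 0.0104 (21%) |
| 19 v 11 | 8/52 × 0.05 = 0.0077 (15%) | 8/52 × 0.09 = 0.0138 (28%) |

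These are the edges of the 95% range. The expected shift is zero, and it is zero for any split if the hospitals do not differ. The 0.0058 shift is 0.0058/0.0177 = 0.33 standard errors.

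**4. Type I error and power.** Simulation of 4,000 runs per scenario: normal outcomes, t-test, N = 104, second-site share 10%, 25% or 50%, difference 0.05 or 0.09. The site recruits in the second half only for the two smaller shares.

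| Allocation | Site in analysis | Type I error | Power at planned effect |
|---|---|---|---|
| One list | No | 4.4–5.6% | 70–79% |
| Stratified by site | No | 3.2–5.1% | 73–79% |
| Either | Yes | about 5% | 79–81% |

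With one list, a chance shift of 1.96 SD is 0.005 to 0.018 mcg/kg/min, or 11–35% of the target effect over these scenarios. Most of the lost power is recovered by the site term; stratifying the list without analysing by site recovers little.

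**5. The rank test.** With 20 late-site patients on one list, the site-stratified rank test (van Elteren) compares with the plain rank-sum test as follows:

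- Sites do not differ: level to within about a point (76–78% for either).
- Difference 0.05: gain of about 1 point.
- Difference 0.09: gain of about 5 points, from roughly 72–73% to 78%.

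**6. Price of separate lists.** For 20 patients on their own list with blocks of 2, 4 and 6, guessing the arm that is behind is right about 70% of the time. On a shared list, staff who see only their own site's patients are right about 53% of the time.

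**The case against.** A reader might infer that both hospitals draw from one shared list. The documents do not establish this. The Randomization paragraph mentions one hospital pharmacy, but the second site's own pharmacy is equally compatible with its own list. What is supported is that allocation at the second site is not described; the ranges above hold only if the list is shared.

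A reader might also infer that site is confounded with arm and the primary result biased. It is not: under randomisation the expected imbalance is zero, and the unadjusted test holds its level.

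The evidence that practice differs is thin. The in-house sepsis guidance cited for the coordinating hospital is said to reflect published campaign guidelines, so it need not be peculiar to that hospital. The sentence on weight-based esmolol at that hospital is a dose rationale and says nothing about vasopressors. The 0.05 difference is assumed and equals the whole planned treatment effect. The SAP's NED mixed model already adjusts for pre-intervention dose, which would absorb much of any baseline site difference, although the primary rank test does not.

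Two practical objections stand. Separate short lists at a small site make the next allocation easier to guess in an unblinded trial. And the SAP, dated December 2020, is written in the past tense and already reports data, so changing the primary test now would be post hoc.

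What survives is that the endpoint depends on clinicians' discretion, two hospitals take part, and neither document uses site.

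**Conclusion.** The point holds as a minor improvement. The protocol should say how the second hospital's patients are allocated, and the analysis should account for site. The cost of leaving things as they are is chance imbalance and some lost precision. With 20 of 104 patients at the late site and a between-site difference of 0.05 mcg/kg/min, an imbalance at the edge of the 95% range moves the estimate by about 0.006, or 12% of the planned effect. Power without a site term is 70–79% over the assumed scenarios, against 79–81% with one. The low end needs half the patients at the second site and a site difference of one full SD.

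All of these sizes rest on three assumptions that the documents do not settle: a shared list, the second site's share, and the between-site difference. The power figures also assume normal outcomes. The documents do not support a claim of systematic bias, of an inflated type I error, or of an actual difference in practice between the hospitals.

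**What to change.** **SAP.** Compare 6-hour NED with a site-stratified rank test (van Elteren) and add site as a fixed effect to the mixed models. If the primary analysis is already fixed or done, keep the rank-sum test as primary, report the site-stratified version as a sensitivity analysis, and add a table of allocation by site and arm.

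**Protocol, only if enrolment is still open.** State in the Randomization paragraph how the second site receives allocations and who holds its list. Stratify the list by site and leave out blocks of two. Dropping them reduces predictability at a small open-label site but does not remove it.

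**Cost.** A little more analysis work and a sentence or two in each document; N = 104 is unchanged. If the lists are split, there is somewhat greater predictability at the smaller site and possibly one more incomplete block at the end of enrolment. When the sites do not differ, the stratified test gives up at most about a point of power.

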Indicate which components(s) or element(s) of your protocol are being changed. Check all applicable items.		
 Principal Investigator	 Study Type (e.g. Phase)	
 Co-Investigators/Study Staff (include Part Q if adding new staff)	 Recruitment, Publicity Materials and/or procedures	
 Study Title	 Consent Procedures	
 Sponsor	 Duration of Subject Participation	
 Application (CCI or sponsor protocol) Content/Version	 Patient Materials (e.g. diaries)	
 Consent Form	 Questionnaires, or Investigator Brochure	
 Local Site Enrollment # of Subjects	 Remuneration	
 Total Enrollment # of Subjects (Multi-Center Trials)	 Research Related Use of Medical Records (Part O)	
 Types of Subjects	 Use of Specimens	
 Source of Subjects	 Research Related Use of Discarded Material (Part N)	
 Other (specify): Part E	 *Study Status Change (i.e., CTE, hold, suspension) *This refers to changes prior to Continuing Review	
Industry Sponsored Protocols only: Sponsor Amendment/Version #:	Revised Protocol Issue Date:	

AMENDMENT ATTACHMENTS

Indicate study documents that have been modified as a result of this amendment and are appended to this application.		
 Revised Protocol (New Version) (1 clean, 1 highlighted)	 New or Revised Advertisement (1 clean, 1 highlighted)	
 Revised Consent Form (1 clean, 1 highlighted)	 Revised Research Participant Materials or Questionnaires (1 clean, 1 highlighted)	
 Other (specify): Part E		

AMENDMENT DESCRIPTION

